## The Total Score shows the severity of depression as following:

0 to 9: No depression or minimal depression

10 to 18: Mild to moderate depression

19 to 29: Moderate to severe depression

30 to 63: Severe depression

BDI will be assessed at each visit from V0 to V6.

Descriptive statistics for BDI total score as well as changes to baseline and 95 % confidence intervals will be presented at each visit. In addition, time profiles of the mean values with SEM will be created.

For BDI item #9 frequency table and shift table to baseline will be presented.

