## 7.3.6. Beck Depression Inventory (BDI)

The BDI scale is currently one of the most widely used instruments in both research and clinical practice for assessing depression, with good reliability and validity, which can be used to document changes brought by therapy. Created by [name] in 1961, and revised in 1996 (BDI-II) for more consistency with the revised DSMIV, it is a 21-question multiple-choice self-report inventory. The questionnaire is composed of items relating to symptoms of depression such as hopelessness and irritability, cognitions such as guilt or feelings of being punished, as well as physical symptoms such as fatigue, weight loss, and lack of interest in sex (Wang , 2013).

Each item has four possible degree of severity rated from 0 to 3, and the patient is asked to choose the one that is closest to how he/she feels. The 21 items are summed linearly to create a score which ranges from 0 to 63. It can be administered as an interview by the clinician or as a self-report instrument.

The suicide item #9 includes the following:

- 0. "I don't have any thoughts of killing myself."
- 1. "I have thoughts of killing myself, but I would not carry them out."
- 2. "I would like to kill myself."
- 3. "I would kill myself if I had the chance."

Total Score Levels of depression (Beck et al, 1988):

- 0 to 9: No depression or minimal depression
- 10 to 18: Mild to moderate depression
- 19 to 29: Moderate to severe depression
- 30 to 63: Severe depression

BDI will be assessed at each visit.

A total score of BDI-21 items  $\ge$ 30 or item 9 >0 results in an exclusion of the patient from further participation in the study.

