## 1.2 Secondary objective

The secondary objectives of the study are:

- To evaluate the safety and tolerability of two doses of SOM3355 (400 mg/day and 600 mg/day) compared with placebo in HD patients, with particular attention to depression and suicidality and to the cardiovascular hemodynamic parameters.
- To evaluate the efficacy of the two doses of SOM3355 (400 mg/day and 600 mg/day) compared with placebo on:
  - o the change of Clinical Global Impression (CGI-C),
  - o the change of Patient Global Impression (PGI-C),
  - o the percentage of responders based on the improvement ≥2 in TMC score,
  - o the percentage of change of TMC score.
- A pharmacokinetic (PK) sub-study in a subset of 24 patients will allow to determine the PK profile of the two doses of SOM3355 (200 mg BID and 300 mg BID) at steady state and to model PK-PD assessments of hemodynamic and cardiac parameters. Analysis of these data will be described in a separate document and the results will be also presented in a separate report.

Statistical Analysis Plan	Version 1.0		Page 7 of 37
Sponsor	SOM Biotech	Protocol No	SOMCT03

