## Descriptive statistics for continuous data

N, mean, SD, min, median and max will be presented. These descriptive statistics will be determined for measured values and for changes from baseline.

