## 4.10.2 Vital signs

The following vital signs parameters will be assessed at each of the visits (from Visit 0 to Visit 6) as per schedule of assessment (except height only at Visit 0).

- Systolic blood pressure (SBP)
- Diastolic blood pressure (DBP)
- Heart rate
- Body weight

Four sequential measures of Blood Pressure should be performed as follows: sitting position for at least 5 minutes, supine position at least 5 minutes, standing position for 1 minute and 3 minutes. Orthostatic BP is calculated as change from supine to standing position after 1 and 3 minutes.

The following summaries will be provided:

- A summary of the observed absolute values and change from baseline in each vital sign parameter by treatment group and time point separately for sitting, supine, 1 min standing and 3 min standing
- A time profiles of the mean values for each vital sign parameter by treatment group separately for sitting, supine, 1 min standing and 3 min standing with SEM

A summary of the incidence of drop in SBP of  $\geq 20$  mmHg or drop in DBP of  $\geq 10$ mm Hg will be presented, where drop in BP is calculated as orthostatic BP.

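### BDI total is summarised only by visit although crossing 30 ends participation, and the SAP specifies no count of patients who ever reach the protocol's BDI, absolute blood-pressure or heart-rate thresholds

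*SAP*

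**What the plan says.** The safety objective in SAP 1.2 singles out these outcomes: "with particular attention to depression and suicidality and to the cardiovascular hemodynamic parameters".

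- **BDI total (SAP 4.10.8).** "Descriptive statistics for BDI total score as well as changes to baseline and 95 % confidence intervals will be presented at each visit". Mean profiles are added. The section prints four severity bands (0–9, 10–18, 19–29, 30–63) but specifies no summary that uses them.
- **BDI item 9 (same section).** "For BDI item #9 frequency table and shift table to baseline will be presented".
- **Vital signs (SAP 4.10.2).** "A summary of the observed absolute values and change from baseline in each vital sign parameter by treatment group and time point", with mean profiles. One threshold summary is added: "A summary of the incidence of drop in SBP of" at least 20 mmHg, or in DBP of at least 10 mmHg, from supine to standing.
- **Descriptive statistics (SAP section 4).** For continuous data, "N, mean, SD, min, median and max will be presented".
- **Removal on BDI (protocol 7.3.6).** A total of 30 or more, or item 9 above 0, "results in an exclusion of the patient from further participation in the study".
- **Withdrawal criteria (protocol 5.7).** The investigator may stop participation for several reasons. They include BDI of 30 or more, blood pressure below 90/60 mmHg, orthostatic hypotension, and heart rate below 50 bpm if sustained and not tolerated.
- **Early leavers (SAP 4.1.2).** The end-of-study value, or a last unscheduled value, is assigned to the first missing visit. If the patient stops exactly at a visit, it is assigned to that visit.
- **Laboratory data (SAP 4.10.4).** The summary of out-of-range values covers every post-baseline value, including unscheduled and early-termination visits.

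**The concern.** A by-visit summary describes the patients still present at that visit. For BDI, whether a patient is still present depends on the BDI value itself, because the protocol takes out those who reach 30. An arm in which more patients become severely depressed loses more of them, and its later visits describe those who did not cross. A reader comparing arms at V5 or V6 could see similar BDI means where the numbers who ever became severely depressed differ.

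Blood pressure and heart rate have a weaker form of the same problem. The protocol names absolute thresholds as grounds for withdrawal, but the SAP specifies a count only for the orthostatic drop. Protocol 2.1.6.1 reports bradycardia and hypotension among the most frequent adverse events in the earlier Huntington's trial. A count of patients who crossed is therefore likely to be wanted when the report is written.

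**Working it through.** The documents give no BDI or blood-pressure means and no event rates, so there is no planned figure to reproduce. The check has two parts.

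**1. Where a threshold value goes**

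I assume that the rule in SAP 4.1.2, which stands under general conventions, also applies to BDI and vital signs.

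| When the crossing is measured | Where it is summarised | Absent from |
|---|---|---|
| At V3, patient stops there | V3 | V4, V5, V6 |
| Between V3 and V4, at the end-of-study visit or a last unscheduled visit | V4 | V5, V6 |
| Between V4 and V5, likewise | V5 | V6 |
| At an unscheduled visit followed by a separate end-of-study visit | No place assigned; the end-of-study value is used | The by-visit summaries |

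The value is therefore usually seen once. It can appear as that visit's maximum BDI or minimum blood pressure. A maximum does not say how many patients crossed, and crossings at different visits are never added up.

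**2. Size, by assumption only**

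Inputs: 43 patients per arm (SAP 1.4). Assumed: *k* = 1, 2 or 4 patients removed; BDI *v* = 30 to 35 at removal; all others present with mean BDI *m* = 8 to 12. For context, the 10% dropout allowance is 0.10 × 43 = 4.3 patients per arm, so *k* = 4 would use almost all of it.

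Mean at a later visit after removal: *m*. Mean if the removal values had been kept: [(43 − *k*)*m* + *kv*] / 43. Difference: *k*(*v* − *m*) / 43.

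- *k* = 1: 1 × (30 − 12)/43 = 0.42 to 1 × (35 − 8)/43 = 0.63 points.
- *k* = 2: 2 × 18/43 = 0.84 to 2 × 27/43 = 1.26 points.
- *k* = 4: 4 × 18/43 = 1.67 to 4 × 27/43 = 2.51 points.

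Patients ever at 30 or more: 1/43 = 2.3%, 2/43 = 4.7%, 4/43 = 9.3%. These percentages do not change with what happens after removal.

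For SBP, assume removal at 88 mmHg and a mean of 115 to 125 mmHg in the others. The later mean is then higher by *k*(*m* − 88)/43:

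- *k* = 1: 27/43 = 0.63 to 37/43 = 0.86 mmHg.
- *k* = 4: 108/43 = 2.51 to 148/43 = 3.44 mmHg.

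The SBP figures also assume that every such patient is withdrawn, which protocol 5.7 does not require.

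**The case against.** A reader might infer that BDI and vital signs are reported only as means, that the worst values disappear, and that the planned safety analysis is therefore biased towards showing no harm. The documents do not support that reading:

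- The by-visit statistics include minimum, median and maximum, so an extreme value shows at its own visit.
- Protocol 5.7 asks for end-of-treatment assessments whenever possible in those who leave, and SAP 4.1.2 places the last value at the first missing visit.
- Orthostatic hypotension, itself a withdrawal criterion, has an incidence summary.
- SAP 4.10.1 tabulates adverse events leading to discontinuation by arm, and SAP 4.2 tabulates withdrawals by reason. Excess harm in one arm should show there.
- Item 9 and the C-SSRS have frequency and shift tables, and the PBA-s has depression and suicidal-ideation items.
- No test or decision rule is tied to the BDI or vital-sign means.
- Withdrawal for blood pressure or heart rate is discretionary, and the heart-rate criterion is qualified.

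A reader might also build a sharp contrast. Suppose 2 to 4 patients rise by 15 points and leave, and nobody else changes. V5 would then show a mean change of 0.0, against 2 × 15/43 = 0.70 to 4 × 15/43 = 1.40 with worst values. This holds only if they leave early enough that no end-of-study value is placed at V5. It also compares a single-visit mean with a worst-of-several mean, which rises through ordinary fluctuation.

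These points limit the claim but do not remove it. Adverse-event and disposition tables depend on how the investigator codes an event or reason; they do not count measured values. Item 9 and the C-SSRS concern suicidality, not depression severity. PBA-s is planned only at V1, V3 and V5 and is likewise summarised by visit. The full list of tables is a separate document (SAP Appendix 1), so such a count may exist there, but the SAP text does not specify one.

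**Conclusion.** The point stands in limited form. It is clearest for BDI total, where protocol 7.3.6 words removal as automatic and triggered by the measured outcome, while the SAP specifies no per-patient count on its own severity bands. By-visit summaries after removal can understate depression in an arm with more removals. It is weaker for absolute blood pressure and heart rate, where withdrawal is a matter of judgement.

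The size of the distortion cannot be derived from the documents. Under the stated assumptions, 2 to 4 removals in an arm of 43 shift a later BDI mean by about 0.8 to 2.5 points and correspond to 4.7% to 9.3% of the arm ever at 30 or more. What does not rest on those assumptions is that a per-patient count over all post-baseline values is unaffected by later removal, and that the SAP already uses this approach for laboratory data.

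**What to change.** In SAP 4.10.8 and 4.10.2 add the following by arm, using all post-baseline values from scheduled, unscheduled and early-termination visits, as SAP 4.10.4 does for laboratory data:

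1. **BDI total:** a shift table from baseline (V1, per SAP 4.1.1) to each patient's worst value on the four listed bands, with the number and percentage ever at 30 or more. The baseline column matters because protocol 5.2 excludes only totals above 30, so a patient could enter at exactly 30.
2. **Vital signs:** the number and percentage ever with SBP/DBP below 90/60 mmHg and ever with heart rate below 50 bpm. Label these as measured-value counts, with a note that protocol 5.7 qualifies the heart-rate criterion as sustained and not tolerated. State whether 90/60 means either or both pressures, and which of the four positional measurements count.

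Read the depression and haemodynamic conclusions from these counts together with the adverse-event tables, with by-visit summaries as support.

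The cost is two extra tables from data already collected. SAP Appendix 1 allows the list of tables to be updated without updating the SAP. Worst-value summaries rise in every arm through ordinary fluctuation, so they should be read only as comparisons between arms.

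Separately, protocol 7.3.6, 5.7 and 2.2.3 must be reconciled. They differ on whether removal is automatic, at the investigator's discretion or expected at once, and on whether item 9 above 0 counts alone or only with active ideation on the C-SSRS.

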#### 4.10.9 ESS assessing sleepiness

The ESS is a self-administered questionnaire comprised of eight questions that provides a measure of a patient's general level of daytime sleepiness. The ESS asks respondents to rate, on a 4-point Likert scale (0-3), their usual chances of dozing off or falling asleep in different situations or activities that most people engage in as part of their daily lives. The total ESS score is the sum of 8 item scores and can range between 0 and 24 with a higher score indicating a higher level of daytime sleepiness.

ESS will be assessed at each visit.

Descriptive statistics for the ESS as well as changes to baseline and 95% confidence intervals will be presented at each visit. In addition, time profiles of the mean values with SEM will be created.

Statistical Analysis Plan	Version 1.0		Page 30 of 37
Sponsor	SOM Biotech	Protocol No	SOMCT03

#### 4.10.10 TFC of the UHDRS® assessing functioning

The UHDRS®-TFC scale is a tool used by clinicians to assess the stage of HD and the level of functional capacity in patients on five items: patients' ability to work, manage finances, run a house, take care of themselves, and live at home independently. The TFC score ranges from 0 (worse) to 13.

TFC will be assessed at screening (Visit 0), at the inclusion (Visit 1), and at the end of maintenance dose (Visit 5 at end of Week 10).

Descriptive statistics for TFC as well as changes to baseline and 95% confidence intervals will be presented at each visit. In addition, time profiles of the mean values with SEM will be created.

#### 4.10.11 **Functional Assessment of the UHDRS®**

The UHDRS®-FA scale includes 25 yes/no questions about common daily tasks (total range 0-25).

FA will be assessed at screening and at the end of the maintenance dose (Visit 5 at end of Week 10).

Descriptive statistics for the FA as well as changes to baseline and 95% confidence intervals will be presented at each visit. In addition, time profiles of the mean values with SEM will be created.

#### 4.10.12 BARS assessing akathisia

The BARS is administered by healthcare providers to assess the severity of drug-induced akathisia and is scored as follows: Objective Akathisia, Subjective Awareness of Restlessness and Subjective Distress Related to Restlessness are rated on a 4-point scale from 0 – 3 and are summed yielding a total score ranging from 0 to 9. Then Global Clinical Assessment of Akathisia uses a 5-point scale ranging from 0-4.

BARS will be assessed at inclusion and at end of the maintenance dose (Visit 5 at end of Week 10).

Descriptive statistics for the BARS as well as changes to baseline and 95% confidence intervals will be presented at each visit. In addition, time profiles of the mean values with SEM will be created.

#### 4.10.13 MoCA scale to assess cognitive disturbances

The MoCA scale is a brief screening instrument recommended for the detection of mild cognitive impairment that is sensitive to executive dysfunction in a variety of neurological conditions. When used in HD, it was more sensitive to detect mild to moderate cognitive impairment.

The items of the MoCA examine attention and concentration, executive functions, memory, language, visuo-constructional skills, conceptual thinking, calculations, and orientation. The attention/executive function items include Trail Making Test B, digit span, target detection, verbal fluency, abstraction, and serial seven subtraction. The visuospatial items include clock drawing and cube copying. The language items include object naming

Statistical Analysis Plan	Version 1.0		Page 31 of 37
Sponsor	SOM Biotech	Protocol No	SOMCT03

and sentence repetition. The memory items include recall of five previously presented words. The orientation items include six orientation-based questions.

MoCA scores range between 0 and 30.

MoCA will be assessed at inclusion and at end of the maintenance dose (Visit 5 at end of Week 10).

Descriptive statistics for the MoCA as well as changes to baseline and 95% confidence intervals will be presented at each visit. In addition, time profiles of the mean values with SEM will be created.

## 4.10.14 PBA-s to assess behavioral symptoms in HD

The PBA short form is the recommended outcome measure for behavioral symptoms in HD. It is a semi-structured interview containing 11 items, each designed to measure the severity and frequency of behavioral neuropsychiatric symptoms that are frequent in HD: depression, suicidal ideation, anxiety, irritability, aggressive behavior, apathy, obsessive-compulsive symptoms, perseverative thinking, paranoid thinking, hallucinations, and disorientation.

Severity and frequency during the previous 4 weeks are rated separately for each symptom on a 5 point (0–4) scale. Severity and frequency ratings are multiplied to provide an overall score for each symptom.

Worst severity rating will be only listed.

PBA-s will be assessed at inclusion, at the interim visit (Visit 3 at the end of Week 6), and at the end of the maintenance dose (Visit 5 at the end of Week 10).

Descriptive statistics for the PBA-s as well as changes to baseline and 95% confidence intervals will be presented at each visit.

#### 4.11 Other variables

Not applicable.

#### 4.12Interim analyses

An unblinded interim analysis for futility (non-binding) will take place when at least half of the total number of planned patients (N = 65) have completed the study or discontinued early. The analysis will be prepared by a separate team that will communicate the results only to designated recipients, e.g., the Steering Committee, to protect the study blind. The primary criterion to assess the futility of the study will be the probability of rejecting the null hypothesis conditional on the accumulated data and the planned sample size. In line with the chosen Holm-Bonferroni multiplicity adjustment, the decision will focus on that hypothesis that yielded the smallest p-value in the interim analysis of the TMC change. A non-binding stop for futility will be recommended if the conditional probability is less than 0.25. Otherwise, the study shall be continued without modification unless otherwise recommended by the SC.

Statistical Analysis Plan	Version 1.0		Page 32 of 37
Sponsor	SOM Biotech	Protocol No	SOMCT03

If a decision is made to stop the trial, then a complete, final analysis will be performed including those patients that were enrolled into the study in the meantime.

The analyses will be performed using the SAS® software (Version 9.4 or later). The method and SAS code will be the same as for primary endpoint described in Section 4.6.1 and Appendix 2.

An unblinded statistician/programmer will perform the unblinded futility analysis. The generated documents will be stored on in a separate file area on the file server with restricted access only to the unblinded person(s).

## **5 QUALITY CONTROL**

The SAP was reviewed by the Trial Statistician (TS) before signature. Particularly the TS has checked the consistency of the described methods and outputs with the actual version of the study protocol. In addition, a sponsor representative has reviewed the SAP before final approval.

Log files of all SAS® programs used in the analysis will be checked for errors, warnings and suspicious notes by the statistical programmer. All findings will be either eliminated or commented upon. The final version of each program will be stored along with its log file in the electronic archive.

All programs will be validated by the program author or an independent statistical programmer depending on the requested validation level selected in the List of TLFs form (FRM/BS/001.02) for a particular program.

The agreement of the program outputs with the SAP, their consistency and plausibility will be checked by the TS. Moreover, the TS will review the outputs regarding completeness, readability and comprehensibility.

The described process is associated with the 'normal' level of program validation. Additional levels of quality control can be specified in the List of TLFs (see Appendix, 1) for individual outputs.

#### **6 DERIVATIONS AND TRANSFORMATIONS**

#### 6.1 Formulas for derived variables

Variable	Definition / Derivation
BMI	Weight [kg] / (height [m])**2
Year of birth	Year of inform consent - Age
Age at HD diagnosis	Year of HD diagnosis - Year of Birth
Age at first symptoms	Year of first symptoms - Year of Birth
Compliance	(Capsules dispensed - capsules returned) / expected number of capsules to be used
CGI-C improvement	Patients with a score of 1 (very much improved), 2 (much improved) or 3 (minimally improved)

Statistical Analysis Plan	Version 1.0		Page 33 of 37
Sponsor	SOM Biotech	Protocol No	SOMCT03

Variable	Definition / Derivation
TMC improvement	change of score between the baseline and the end of mainte-
	nance dose is $\geq$ - 2
PGI-C improvement	patients with a score of 1 (very much improved), 2 (much im-
_	proved) or 3 (minimally improved)

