#### 3.2. PRIMARY EFFICACY ENDPOINT

The primary measure of efficacy will be the change in TMC sub-score of the UHDRS® between baseline and end of maintenance dose (the mean of Visit 4 and Visit 5 minus the mean of Visit 0 and Visit 1).

The TMC score is a standardized, reliable chorea assessment based on frequency and severity in 7 body regions.

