#### 3.3. SECONDARY EFFICACY ENDPOINTS

Key secondary efficacy endpoint:

• Change from baseline in Clinical Global Impression (CGI-C),

Other secondary efficacy endpoints:

- Change from baseline in Patient Global Impression (PGI-C).
- TMC-response defined as improvement ≥2 in TMC score between baseline and end of

maintenance dose.

- Percentage of change in TMC score between baseline and the end of maintenance dose.
- Change from baseline in Total Motor Score (TMS) of the UHDRS®.
- Change from baseline in Gait sub-score of the UHDRS®.
- Change from baseline in Dystonia sub-score of the UHDRS®.
- Change from baseline in EQ5D-5L measuring quality of life.

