#### 7.2. EFFICACY ASSESSMENTS

# 7.2.1. Total Maximal Chorea score (TMC) of the UHDRS®

The TMC score is part of the motor assessment of the UHDRS® consist of the sum of the seven body regions used to assess chorea including the face, oral-buccal-lingual region, trunk and each limb independently. Each territory is scored from 0 (normal findings) to 4 indicating severe abnormalities (0=absent, 1=slight/intermittent, 2=mild, 3=moderate/ common, 4=marked prolonged). The minimum TMC score is 0 (absent) and the maximal score is 28. A decrease in score indicates improvement in chorea.

This scale, which specifically targets a single motor feature in HD (chorea) and has been validated for this purpose, is more adequate in assessing for a specific symptomatic treatment indication.

TMC score will be assessed at each visit.

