## 2.2 Deviations from the trial protocol with regard to statistical analyses

The following deviations from the protocol were identified as being important for the statistical analysis:

For the key secondary efficacy endpoint (Change from baseline in the Clinical Global Impression (CGI-C)) multiplicity adjustment will be applied.

Original text in protocol: The type I error will be set at 0.05 (two-sided) and the coverage level of confidence intervals to 95% for all secondary efficacy analyses. No multiplicity adjustment will be applied for the statistical inferences of the secondary efficacy endpoints.

Statistical Analysis Plan	Version 1.0		Page 9 of 37
Sponsor	SOM Biotech	Protocol No	SOMCT03

The revised definition in SAP only for key secondary endpoint: To preserve the family-wise error rate at the 0.05 level when comparing the two doses of SOM3355 versus placebo and comparing a primary endpoint and key secondary endpoint, statistical testing will be carried out using the Holm procedure for CGI-C if the primary endpoint is significant for both doses. The smallest p-value of the two comparisons will be first compared at the two-sided 0.025 level and if statistically significant, the other p-value will be compared at the two-sided 0.05 level.

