## Listings

All recorded data will be listed by patient (sorted by treatment group Placebo, 200 mg BID, 300 mg BID). Identification variables are centre number, patient number and treatment group.

Derived data will be stored in special analysis data sets and will be calculated as outlined in section 6.1.

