## 4.7.2.2 Percentage of responders on TMC score

TMC score is assessed at each visit from V0 to V6.

V0 and V1 values are used to calculate the baseline (mean of the 2 values), and V4 V5 values for the end of maintenance dose.

Assessment at V6 occurs after the drug interruption with one week at 200 mg OD and the last week under placebo.

TMC score evolution will be assessed at each visit.

The number and percentage of responders with an improvement of at least 2 points in the TMC score will be calculated in each treatment group at each visit.

The TMC response status ("Responder" vs. "Not responder") will be described at each visit.

Logistic regression model will be performed for responders on TMC score at V5 (end of maintenance dose) including the treatment group as the main factor in the model. Estimates along with 95% confidence intervals for the difference in response proportion and the odds ratio of response will be derived from this model.

In addition, histogram will be presented.

This analysis will be repeated on the PP population.

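### SAP 6.1 reverses the inequality for TMC improvement (change ≥ −2 instead of ≤ −2), so literal programming would turn the responder comparison against the drug

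*SAP*

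**What the plan says.** The TMC improvement row of SAP 6.1 reads "change of score between the baseline and the end of mainte" and, after the line break, "nance dose is $\geq$ - 2". SAP section 4, under Listings, gives that table its force: "Derived data will be stored in special analysis data sets and will be calculated as outlined in section 6.1".

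Elsewhere the documents fix the sign and the threshold:

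- **Direction of change.** Protocol 3.2 defines it as "the mean of Visit 4 and Visit 5 minus the mean of Visit 0 and Visit 1". SAP 4.7.1 uses the same subtraction, and SAP 4.7.2.3 uses the same direction for percentage change.
- **Direction of the scale.** Protocol 7.2.1: "A decrease in score indicates improvement in chorea".
- **Response.** Protocol 3.3: "TMC-response defined as improvement ≥2 in TMC score between baseline and end of" maintenance. Protocol 9.4.2 and SAP 4.7.2 agree, and SAP 4.7.2.2 says "The number and percentage of responders with an improvement of at least 2 points in the TMC score will be calculated".

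SAP 2.2, introduced by "The following deviations from the protocol were identified as being important for the statistical analysis", lists only the multiplicity change for CGI-C. It records no redefinition of TMC response.

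**The concern.** Two parts of a final SAP give opposite rules for one endpoint, and the wrong one sits in the table that programmers are told to follow. TMC response is a named secondary objective (Protocol 3.1, SAP 1.2). It comes first among the other secondary endpoints in SAP 4.7.2, and its analysis is repeated on the per-protocol population. If the analysis data set follows 6.1 literally, a drug that reduces chorea would show a lower response rate than placebo.

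There is also a smaller wording point on the same endpoint. SAP 4.7.2.2 bases the end of maintenance on Visits 4 and 5, but then places the logistic model at V5. The visit basis of the modelled variable is therefore unclear.

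**Working it through.** **The rule on individual values.** Let change = end of maintenance − baseline. An improvement of at least 2 means baseline − end ≥ 2, that is, change ≤ −2. Illustrative values:

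| Change | Intended (≤ −2) | SAP 6.1 (≥ −2) |
|---|---|---|
| +5 | no | yes |
| 0 | no | yes |
| −2 | yes | yes |
| −3 | yes | no |

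The two rules agree only at exactly −2.

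**The plan's own figure.** The documents plan no responder rate; their only power figure is for the primary endpoint (Protocol 9.3). With difference 2.5, SD 3.5 and two-sided alpha 0.025, the two-sample t-test has 79.4% power at 38 per arm and 80.5% at 39. The stated 39 is therefore reproduced. The same difference and SD are used below.

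**Inputs for the response rates.**
- Effect −2.5 and SD 3.5 (Protocol 9.3), with SD 3.9 as the other value given in Protocol 9.2.
- Placebo mean change m: not in the documents; assumed and varied over 0, −1 and −2. Active mean = m − 2.5.
- Normal model on a half-point grid, since change is a difference between two averages of two whole-number scores.

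**Formulas**, with μ the arm mean:
- Intended: P(change ≤ −2) = Φ((−1.75 − μ)/SD)
- Literal 6.1: P(change ≥ −2) = 1 − Φ((−2.25 − μ)/SD)

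**Worked case, m = −1, SD 3.5** (active mean −3.5):
- Intended: active Φ(1.75/3.5) = Φ(0.500) = 69.1%; placebo Φ(−0.75/3.5) = Φ(−0.214) = 41.5%; odds ratio 3.16.
- Literal: active 1 − Φ(1.25/3.5) = 1 − Φ(0.357) = 36.0%; placebo 1 − Φ(−0.357) = 64.0%; odds ratio 0.32.

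**All scenarios (active v placebo):**

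| SD | Placebo mean (assumed) | Intended rule | OR | Literal 6.1 | OR |
|---|---|---|---|---|---|
| 3.5 | 0 | 58.5% v 30.9% | 3.16 | 47.2% v 74.0% | 0.31 |
| 3.5 | −1 | 69.1% v 41.5% | 3.16 | 36.0% v 64.0% | 0.32 |
| 3.5 | −2 | 78.4% v 52.8% | 3.24 | 26.0% v 52.8% | 0.31 |
| 3.9 | 0 | 57.6% v 32.7% | 2.80 | 47.4% v 71.8% | 0.35 |
| 3.9 | −1 | 67.3% v 42.4% | 2.80 | 37.4% v 62.6% | 0.36 |
| 3.9 | −2 | 76.0% v 52.6% | 2.85 | 28.2% v 52.6% | 0.35 |

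The share of patients at exactly −2, the only ones classed correctly by the literal rule, is about 4% to 6% per arm.

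**Chance of a significant result against the drug under literal coding.** Binomial simulation with 200,000 draws per scenario, a Wald test of the log odds ratio at two-sided 0.05, and 39 or 43 per arm: about 69–73% at SD 3.5 and about 60–63% at SD 3.9. With correct coding at SD 3.5, 66–72% of trials are significant in favour of the drug.

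**Visit basis.** In a bivariate normal simulation with assumed Visit 4–Visit 5 correlations of 0.7 to 0.9, using Visit 5 alone instead of the two-visit mean changes the status of about 6–12% of patients. It moves arm-level rates by at most about 1.5 percentage points.

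**The case against.** The strongest reply is that this is a slip of notation. The rule is worded correctly throughout the protocol and in the SAP section that specifies the model. The 6.1 row is itself labelled as improvement, so the natural reading is an improvement of 2 or more, shown as −2. SAP section 5 requires program validation and a check of outputs for consistency and plausibility. Literal coding would clash visibly with the TMC descriptives, the MMRM and the percentage-change analysis.

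Much of this stands. The intent is clear, the harm depends on literal coding, and the documents give no probability for that. The simulated percentages describe what would follow from literal coding; they are not an expected result of the plan.

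It does not remove the error. SAP section 4 names 6.1 as the source for derived data. Section 5 checks outputs against the SAP, and a literal program agrees with 6.1. It also allows the program's author to validate it. Section 5 further says that consistency with the protocol was checked before signature, yet the line remains.

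The symbol comes from machine-read text with a detached dash. If the dash were only typographic, change ≥ 2 would still be wrong for a signed change, because it would select worsening. The objection that the Visit 5 wording is a minor matter is fair, and it is treated here as a clarification.

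**Conclusion.** The concern holds and should be fixed before the responder variable is programmed. SAP 6.1 is wrong for the signed change it names and contradicts every other definition of TMC response in the two documents. If followed literally, it turns an odds ratio of about 3.2 in favour of active into about 0.31 at SD 3.5 (about 2.8 into about 0.35 at SD 3.9).

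The rates rest on a normal model, the plan's effect of −2.5 and an assumed placebo mean change. The reversal occurred at every assumed mean and at both SDs; it does require that the drug lowers TMC relative to placebo, as the plan assumes. The primary MMRM, the Holm procedure, the key secondary CGI-C, the sample size and the futility rule are unaffected.

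**What to change.** First check the symbol against the signed SAP. Then:

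- **SAP 6.1:** define a responder as [(TMC V4 + TMC V5)/2 − baseline TMC] ≤ −2. If only one of Visits 4 and 5 is available, use that visit, as SAP 4.7.1 does for the primary endpoint. State this explicitly, because 4.7.2.2 does not. For the by-visit tables, apply the same inequality to the change at that visit.
- **SAP 4.7.2.2:** state that the end-of-maintenance logistic model uses this variable, so that the references to Visits 4 and 5 and to V5 agree.

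The cost is one inequality sign and a line or two of clarification. No new data are needed and no other analysis changes.
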